#### **2.6.3.1.1 Overview of Solicited ARs**

An overall summary of solicited ARs up to 7 days after study injection (with a toxicity grade of Grade 1 or greater) including the number and percentage of participants, along with the number of events, by vaccination group (as defined in Section 2.6.1) will be presented.

The number and percentage of subjects experiencing any solicited local ARs and solicited systemic ARs of Grade 3 or higher will be provided.

#### **2.6.3.1.2 Solicited ARs by Toxicity Grade**

An summary of solicited ARs up to 7 days after study injection (with a toxicity grade of Grade 1 or greater) by toxicity grade, including the number and percentage of participants, by vaccination group (as defined in Section 2.6.1) who experience the following will be presented:

- Any solicited ARs,
- Any solicited systemic AR,
- Any solicited local AR,
- Each individual solicited systemic and local AR,

A 2-sided 95% exact CI using the Clopper-Pearson method will also be provided for the percentage of participants with any solicited AR (overall and local, systemic). An additional description for Grade 3 or Above (Grade  $\geq 3$ ) will be provided for all above categories.

A summary figure will be produced for local and systemic event rates by toxicity grade.

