### 2.1. Study Objectives

#### 2.1.1. Primary Objectives

The primary objective is to evaluate the safety and reactogenicity of study intervention administration across study treatment arms.

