### **3.3. Study Design**

#### **3.3.1. Overall Study Design**

[figure not shown]
**Part 2** of the study will be a Phase 2 randomized, stratified, observer-blind, active-control study to evaluate the safety, reactogenicity, and immunogenicity of mRNA-1083 compositions and dose levels compared with active-control vaccines mRNA-1010, mRNA-1283.815, mRNA-1273.815, and licensed active-control vaccine, Fluarix in healthy adults  $\geq 18$  to  $<50$  years of age. Approximately 520 participants  $\geq 18$  to  $<50$  years of age will be enrolled. Participants will be randomized (in equal allocation ratio) into the investigational treatment arms, stratified by influenza vaccine status in the most recent influenza season (received or not received since Sept 2023). Table 9 lists the details of study cohorts and dose levels for study vaccine administration. All participants will receive a single IM injection of study intervention administered in a deltoid muscle on Day 1.

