**Table 10 Sample Size Determination (Part 2)**

Sample Size	True AE Rate	Probability of 0 AEs	Power to Detect at Least 1 AE
40	2.0%	44.6%	55.4%
40	3.0%	29.6%	70.4%
40	4.0%	19.5%	80.5%
40	5.0%	12.9%	87.1%

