### **3.3.4. Randomization**

Participants will be randomized (in equal allocation ratio) into the investigational treatment arms, stratified by influenza vaccine status in the most recent influenza season (received or not received since Sept 2023).

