### 3.6.1. General Considerations

See Section 2.6.1 for details.

**For calculation regarding antibody levels/titers**, antibody values reported as below the lower limit of quantification (LLOQ) will be replaced by  $0.5 \times \text{LLOQ}$ . Values reported as above the upper limit of quantification (ULOQ) will be converted to the ULOQ. Missing results will not be imputed.

**Table layouts** will be presented according to vaccination group. First for the overall participants, then by subgroups as given in Table 13.

For Part 2, the following vaccination groups will be used for summary purposes for tables and figures outputs:

- Fluarix
- mRNA-1010 [REDACTED]  $\mu\text{g}$
- mRNA-1010 [REDACTED]  $\mu\text{g}$
- mRNA-1273.815 [REDACTED]  $\mu\text{g}$
- mRNA-1283.815 [REDACTED]  $\mu\text{g}$
- mRNA-1083 [REDACTED]  $\mu\text{g}$
- All mRNA-1083 [REDACTED] (all mRNA-1083 [REDACTED] vaccination groups combined; applicable to safety and reactogenicity analyses only)
- All mRNA-1083 [REDACTED] (all mRNA-1083 [REDACTED] vaccination groups combined; applicable to safety and reactogenicity analyses only)
- Overall (All vaccination groups combined; details are available below)

The “Overall” combined group will be presented for baseline summaries such as participant disposition, demographic summaries, concordance of randomization stratum, etc. as well as

major protocol deviation, medical history, concomitant medication and study duration summaries.

**Subgroups:** For Part 2, the following subgroups will be used for summary purposes, where indicated in this SAP. Unless otherwise specified, all subgroups are based on eCRF.

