#### **3.6.3.1.2 Solicited ARs by Toxicity Grade**

See Section 2.6.3.1.2 for details.

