**Table 14 Covariates Included in Different ANCOVA Models (Part 2)**

Assay	Subgroup	Covariate(s)
PsVNA	Overall	Log-transformed baseline antibody value, Influenza Vaccine Status Since Sept 2023 (IRT)
	Overall	Log-transformed baseline antibody value
	Covid Vaccine Status Since Sept 2023: Received	Log-transformed baseline antibody value
	Covid Vaccine Status Since Sept 2023: Not Received	Log-transformed baseline antibody value
	Baseline SARS-CoV2 Status: Positive	Log-transformed baseline antibody value
	Baseline SARS-CoV2 Status: Negative	Log-transformed baseline antibody value
HAI	Overall	Log-transformed baseline antibody value, Influenza Vaccine Status Since Sept 2023 (IRT)
	Overall	Log-transformed baseline antibody value, Influenza Vaccine Status Since Sept 2023 (EDC)
	Influenza Vaccine Status Since Sept 2023 (EDC): Received	Log-transformed baseline antibody value
	Influenza Vaccine Status Since Sept 2023 (EDC): Not Received	Log-transformed baseline antibody value

For each pair of between-group comparison specified in Table 15, the GMR between the two treatment groups in each pair will be estimated from the ANCOVA model, with its 2-sided 95% CI provided accordingly.

Seroconversion rate (SCR) for influenza from Baseline will be summarized at Day 29 with its 2-sided 95% CI using the Clopper-Pearson method for participants in the groups receiving mRNA-1083, mRNA-1010 or Fluarix.

- SCR at Day 29 is defined as the percentage of participants with a Day 29 titer **CCI** if Baseline is **CCI** or a 4-fold or greater rise if Baseline is **CCI** in anti-HA antibodies measured by HAI assay

Seroresponse rate (SRR) for SARS-CoV-2 from Baseline will be summarized at Day 29 with its 2-sided 95% CI using the Clopper-Pearson method for participants in the groups receiving mRNA-1083, mRNA-1283.815 or mRNA-1273.815.

- SRR at Day 29 is defined as the proportion of participants with a Day 29 titer  $\geq$  4-fold if Baseline is  $\geq$  LLOQ or  $\geq 4 \times$  LLOQ if Baseline titer is  $<$  LLOQ in nAb titers measured by PsVNA.

Additional comparisons or analysis statistics will be provided by treatment arm at Day 29 for the influenza and SARS-CoV-2 endpoints. For each pair of between-group comparison specified in Table 15, the difference of seroresponse/seroconversion rate (SRR/SCR) between the two treatment groups in each pair will be provided, with its 2-sided 95% CI estimated using Miettinen-Nurminen method.

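### No between-arm estimate with an interval is planned for any safety or reactogenicity endpoint; a short list of descriptive risk differences would fill the gap in Part 2

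*SAP*

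**What the plan says.** SAP 3.3.1 describes Part 2 as a randomised, active-control study "to evaluate the safety, reactogenicity, and immunogenicity of mRNA-1083 compositions and dose levels compared with active-control vaccines"; SAP 2.3.1 uses the same wording for Part 1. Allocation is equal: 13 arms of 40 in Part 2 ("Participants will be randomized (in equal allocation ratio) into the investigational treatment arms", SAP 3.3.4), and 12 arms per cohort in Part 1, with 50 per arm in Cohort A and 52 in Cohort B.

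For Part 1, "The primary objective is to evaluate the safety and reactogenicity of study intervention administration across study treatment arms" (SAP 2.1.1), and all its primary endpoints are safety endpoints (SAP 2.2.1). Part 2 has a second primary objective, Day 29 humoral immunogenicity (SAP 3.1.1).

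On solicited adverse reactions (ARs), SAP 2.6.3.1.2 plans counts and percentages by vaccination group and toxicity grade. It then adds: "A 2-sided 95% exact CI using the Clopper-Pearson method will also be provided for the percentage of participants with any solicited AR", overall and for local and systemic reactions. Grade 3 or above gets an additional description, with no interval clearly specified. For Part 2, SAP 3.6.3.1.2 reads only "See Section 2.6.3.1.2 for details". Protocol 9.5.3 and Table 11 match this: a CI is ticked for any solicited AR and for no other safety endpoint.

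The immunogenicity plan goes further. For the arm pairs in SAP Table 15, SAP 3.6.4.1 plans geometric mean ratios with 95% CIs. It also states that "the difference of seroresponse/seroconversion rate (SRR/SCR) between the two treatment groups in each pair will be provided", with a Miettinen-Nurminen interval. SAP 3.6.1 forms two pooled mRNA-1083 groups ("vaccination groups combined; applicable to safety and reactogenicity analyses only"), but plans no estimate of either against a comparator.

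**The concern.** Randomisation to concurrent controls supports an estimate of a difference. For reactogenicity the plan stops at one estimate per arm, so the reader must form the difference and has no stated uncertainty for it.

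This matters because the arms have to be weighed against each other. Protocol 1.1 gives the purpose of Part 1 as selecting a composition and dose level for Phase 3, and that of Part 2 as generating safety and immunogenicity data on further compositions and dose levels in adults under 50. Protocol 2.1.1 reports that, in the Part 1 mRNA-1083 arms, participants aged 18 to under 50 had solicited ARs more often than the older groups. In Part 2 the immune response will be reported as differences with intervals and the reactogenicity will not. A reader who sets two one-arm intervals side by side may take overlap to mean similarity, which is a much weaker check than an interval for the difference.

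**Working it through.** **1. The plan's own figure.** SAP Tables 2 and 10 (Protocol Tables 8 and 9) give the chance of at least one AE in one arm, 1 − (1 − p)^n.
- n = 40: 1 − 0.96^40 = 80.5% and 1 − 0.95^40 = 87.1%, as stated.
- n = 50: 1 − 0.96^50 = 87.0% and 1 − 0.95^50 = 92.3%, as stated.

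These are one-arm quantities. No between-arm precision is stated for reactogenicity.

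**2. Methods.** Both are already in the SAP.
- Clopper-Pearson limits for x of n: the 2.5% point of Beta(x, n − x + 1) and the 97.5% point of Beta(x + 1, n − x).
- Miettinen-Nurminen limits: the values d for which (p1 − p2 − d) / √{[r1(1 − r1)/n1 + r2(1 − r2)/n2] × N/(N − 1)} = ±1.96. Here p1 and p2 are the observed proportions, r1 and r2 are the maximum likelihood proportions constrained to r1 − r2 = d, and N = n1 + n2.

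The documents give no AR rates by arm, so every rate below is an assumption.

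**3. What the two kinds of interval show at 40 per arm.**
- 10/40 versus 2/40: exact CIs 12.7 to 41.2% and 0.6 to 16.9%, which overlap. Difference 20 points, 95% CI 4.8 to 36.2.
- 28/40 versus 20/40: exact CIs 53.5 to 83.4% and 33.8 to 66.2%, which overlap. Difference 20 points, 95% CI −1.6 to 39.9. Here the difference interval also includes zero, but it shows that an excess of nearly 40 points is not ruled out.

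**4. Precision of the added estimate.** Half-width is (upper − lower)/2.
- 40 per arm, 28 v 20: (39.9 + 1.6)/2 = 20.8 points.
- 52 per arm, 47 v 36: (36.3 − 6.0)/2 = 15.2 points.
- Pooled composition, 112/160 v 20/40: CI 3.3 to 36.5, half-width 16.6 points. The 160 assumes four arms per composition (4 × 40).

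So single-arm pairs give about ±15 to 21 points at assumed rates of 50 to 90%. At 40 per arm, the difference that a two-sided 95% comparison would detect with 80% probability is about 31, 30 and 24 points for control rates of 30, 50 and 70%.

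**5. How much a reader loses by judging on overlap.** Exact enumeration over both binomials gives the chance that the score comparison (Miettinen-Nurminen variance at d = 0) excludes zero, against the chance that the two exact CIs do not overlap:

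| Assumed true rates | 40 v 40: difference | 40 v 40: non-overlap | 160 v 40: difference | 160 v 40: non-overlap |
|---|---|---|---|---|
| 25% v 5% | 76% | 29% | 90% | 63% |
| 30% v 10% | 63% | 22% | 81% | 48% |
| 80% v 50% | 82% | 45% | 96% | 80% |
| 70% v 50% | 46% | 12% | 66% | 32% |
| 15% v 5% | 35% | 4% | 38% | 11% |

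With equal rates of 5, 10, 50 or 80% at 40 v 40, non-overlap occurs in 0.02 to 0.25% of cases, and the difference interval excludes zero in about 4 to 6%.

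**6. Size of the added table in Part 2.** A full grid would be 10 mRNA-1083 groups (8 arms, 2 pooled) × 5 comparator arms × 4 endpoints = 200 intervals. The restricted list under the fix is 2 pooled × 5 comparators + 8 arms × 2 licensed comparators = 26 contrasts; × 4 endpoints = 104 intervals. If no true differences existed, 4 to 6% of 104 is about 4 to 6 intervals excluding zero, and many share arms.

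**The case against.** The strongest answer is that this is a declared choice. Protocol 9.2 plans no formal testing for safety and reactogenicity and sizes the trial for a descriptive summary. Protocol 9.6.1 repeats that the analyses are descriptive, and Protocol 9.5.1 plans between-group comparisons for immunogenicity only. Safety is to be judged by clinical review (Protocol 9.5.3, SAP 2.6.3). By-arm tables let anyone subtract two percentages, and the pooled groups appear beside the comparators. All of that stands, and it is why this is an improvement rather than an error. It does not exclude an unadjusted difference with an interval, which is estimation; the SAP already reports the same quantity for seroconversion and seroresponse.

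It also stands that no section tells anyone to judge by overlap, so step 5 describes a reader's likely shortcut and not a rule of the plan. The 25% v 5% row resembles a Grade 3 outcome, for which one-arm intervals may not be produced at all. For smaller true differences the added interval will usually include zero too.

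Two stronger readings are tempting. One is that the randomised arms are never compared on any primary endpoint. That is true of Part 1 but not of Part 2, where Table 15 sets out comparisons on primary Day 29 immunogenicity. The other is that the column heading "Power to Detect at Least 1 AE" in SAP Table 10 claims between-arm power. The text beside it speaks only of the probability of observing at least one AE, so the label is cosmetic.

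**Conclusion.** The gap is real and modest. Neither part plans a between-arm estimate with an interval for any safety or reactogenicity endpoint. Nothing planned is invalid and the documents do not contradict themselves, but the one-arm intervals leave unquantified the differences from active controls that the design is meant to evaluate.

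The practical size depends on AR rates that the documents do not give. For assumed true differences of 20 to 30 points at 40 per arm, an interval for the difference would exclude zero in 46 to 82% of trials, against 12 to 45% for non-overlap of exact intervals. For a 10-point difference (15% v 5%) neither is informative as a decision rule (35% and 4%); the value of the interval is then in showing how large an excess remains possible.

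The case is strongest for Part 2. The Part 1 interim results are already described in Protocol 2.1.1, and Protocol section 2 says that the Phase 3 study had completed enrolment by November 2023, so an addition to Part 1 could no longer be prespecified.

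**What to change.** In SAP 3.6.3.1.2, before Part 2 is unblinded if that is still possible, add a descriptive difference in percentage with a two-sided 95% Miettinen-Nurminen CI for four summaries: any solicited local AR, any solicited systemic AR, and each of these at Grade 3 or above. Use the Solicited Safety Set, as treated, with no multiplicity adjustment, and say so in the table footnote.

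Limit it to a prespecified list: each pooled mRNA-1083 composition group versus each comparator arm, and each individual mRNA-1083 arm versus the two licensed comparators (Fluarix and mRNA-1273.815). That is 26 contrasts. If the same table is produced for Part 1, label it as added after the interim results were known.

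The cost is SAP wording and one table of 104 intervals, from data already collected and a method already programmed for seroconversion and seroresponse. No participants or procedures are added. The downside is that the intervals are unadjusted, wide for single-arm pairs, and will in a few cases exclude zero by chance, so the footnote should warn against reading them as tests.

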#### **2.6.3.1.3 Solicited ARs by Onset Day**

An summary of solicited ARs up to 7 days after study injection (with a toxicity grade of Grade 1 or greater) by onset day (from Day 1 through Day 7), including the number and percentage of

participants, by vaccination group (as defined in Section 2.6.1) who experience the following will be presented:

- Any solicited ARs,
- Any solicited systemic AR,
- Any solicited local AR,
- Each individual solicited systemic and local AR,

The onset of individual solicited AR is defined as the time point after injection (Section 2.6.1) at which the respective solicited AR first occurred.

#### **2.6.3.1.4 Characteristics of Solicited ARs**

A descriptive summary of the day of onset and the duration of solicited ARs up to 7 days after study injection (with a toxicity grade of Grade 1 or greater), by vaccination group (as defined in Section 2.6.1) who experience the following will be presented:

- Any solicited ARs,
- Any solicited systemic AR,
- Any solicited local AR,
- Each individual solicited systemic and local AR

The onset of individual solicited AR is defined as the time point after injection (Section 2.6.1) at which the respective solicited AR first occurred. The duration calculation method is available in the Section 2.6.1 as well.

#### **2.6.3.1.5 Other solicited ARs summaries**

A summary of solicited ARs persisting beyond 7 days after study injection (with a toxicity grade of Grade 1 or greater) by grades, including the number and percentage of participants, by vaccination group (as defined in Section 2.6.1) who experience the following will be presented:

- Any solicited ARs,
- Any solicited systemic AR,
- Any solicited local AR,
- Each individual solicited systemic and local AR.

Solicited local and systemic ARs (with a toxicity grade of Grade 1 or greater) will be provided in listings. Medications taken to prevent or treat pain or fever will also be presented. All solicited ARs that continue beyond 7 days post-injection (with a toxicity grade of Grade 1 or greater) will be listed as well.

### **2.6.3.2. Unsolicited Treatment-Emergent Adverse Events**

A treatment-emergent AE (TEAE) is defined as any event occurring during the study not present before exposure to IP or any event already present that worsens in intensity or frequency after exposure to IP.

An unsolicited TEAE is any AE reported by the participant that is not specified as a solicited AR in the protocol or is specified as a solicited AR but starts outside the protocol-defined period for reporting solicited ARs (i.e., 7 days after study vaccine administration). For analysis and reporting purposes, unsolicited TEAEs will include the following:

- TEAEs that are reported by participants and recorded on the AE eCRF
- Solicited ARs that meet SAE criteria after injection are recorded on the Reactogenicity eCRF

Unsolicited AEs include serious (SAE) and nonserious AEs. Worsening of a pre-existing condition after vaccination will be reported as a new AE.

A MAAE is an AE that leads to an unscheduled visit to a healthcare professional (HCP). This would include visits to a study site for unscheduled assessments (e.g., rash assessment, abnormal laboratory follow-up) and visits to HCPs external to the study site. An AESI is an AE (serious or nonserious) of scientific and medical concern specific to the Sponsor's product or program for which ongoing monitoring and immediate notification by the Investigator to the Sponsor is required and documentation is in the form of a case narrative. Such events may require further investigation to characterize and understand them.

All unsolicited AEs reported or observed during the clinical trial will be collected from start of study intervention through 28 days after injection. All AEs leading to study discontinuation, MAAE, SAEs, and AESIs will be collected from the start of study intervention administration until through EoS or discontinuation from the clinical trial.

Unsolicited AEs will be coded according to Medical Dictionary for Regulatory Activities (MedDRA) version 26.0 or higher and presented by MedDRA system organ class (SOC) and preferred term (PT).

Analyses of unsolicited TEAEs will be provided (1) for up to 28 days after vaccination and (2) until EoS visit unless otherwise specified (as defined in Section 2.6.1). SOC will be displayed in an internationally agreed order. PT will be displayed in descending order of frequency of the combined:

- 1083.2 treatment group (mRNA-1083.2 **CCI**  $\mu$ g, mRNA-1083.2 **cci**  $\mu$ g, and mRNA-1083.2 **cc**  $\mu$ g), and then alphabetically within each SOC.

When summarizing the number and percentage of participants with an event, participants with multiple occurrences of the same AE or a continuing AE will be counted once. Only the maximum severity level will be presented in the severity/toxicity summaries, and the strongest relationship level will be presented in the relationship summaries.

For the by-severity summaries, the toxicity grade of a solicited AR meeting SAE criteria will be mapped to a severity level of Mild/Grade 1, Moderate/Grade 2, or Severe/ $\geq$  Grade 3, and the maximum severity level in the case of multiple events will be presented.

The following listings containing individual participant AEs data will be provided:

- Any unsolicited AEs,
- Any treatment-related unsolicited AEs,
- Unsolicited serious AEs,
- Unsolicited serious treatment-related AEs,
- Unsolicited severe AEs
- Unsolicited AEs leading to discontinued from the study,
- Unsolicited MAAEs,
- Unsolicited AESIs,

Treatment-emergent AEs will be flagged in all data listings.

In addition, number of participants with occurrences of selected TEAEs of clinical interests identified by SMQ will be summarized up to 28 days after injection and throughout the study.

SMQ will be summarized by PT, if applicable. Detailed description of SMQ is presented in Appendix H. A listing of unsolicited AEs by SMQ will be provided.

### **2.6.3.2.1 Overview of Unsolicited TEAEs**

An overall summary of unsolicited TEAEs, including the number and percentage of participants, by vaccination group (as defined in Section 2.6.1) who experience the following will be presented:

- Any unsolicited AEs,
- Any unsolicited serious AEs,
- Any unsolicited AESI,
- Any unsolicited AEs that are medically attended,
- Any unsolicited AEs leading to study discontinuation,
- Any unsolicited severe ( $\geq$  grade 3) AEs,
- Any unsolicited AEs that are fatal.

The table will also include number and percentage of participants with unsolicited TEAEs that are treatment-related in each of the above categories.

### **2.6.3.2.2 TEAEs by System Organ Class and Preferred Term**

The following summary tables of TEAEs will be provided by SOC and PT using frequency counts and percentages (i.e., number and percentage of participants with an event) and number of events by vaccination group (as defined in Section 2.6.1):

- All unsolicited AEs,
- All unsolicited AEs that are treatment-related,
- All unsolicited serious AEs,
- All unsolicited serious AEs that are treatment-related,
- All unsolicited AESI,
- All unsolicited AESI that are treatment-related,
- All unsolicited AEs that are medically attended,
- All unsolicited AEs that are medically attended that are treatment-related,
- All unsolicited severe (grade  $\geq$  3) AEs,

- All unsolicited severe (grade  $\geq 3$ ) AEs that are treatment-related,
- All unsolicited AEs leading to study discontinuation,

